6.3. Clinical Laboratory Parameters

Number of subjects with clinically significant value for selected laboratory parameters as defined in [Table 5](#) at any post-baseline visit, including unscheduled visits, will be summarized for double-blind period and for on-vatiquinone period.

Table 5: Criteria for Clinically Significant for Selected Laboratory Parameters

Category	Laboratory Parameters	Criteria
Elevated AST or ALT	AST and ALT	ALT or AST $\geq 3 \times \text{ULN}$
Elevated INR	INR	INR $\geq \text{ULN}$ INR $\geq 1.5 \times \text{ULN}$
Elevated serum creatinine	Serum creatinine	Serum creatinine $\geq 1.5 \times \text{ULN}$

Abbreviations: ALT, alanine aminotransferase; AST, aspartate aminotransferase; INR, international normalized ratio; ULN, upper limit of normal.

Lab parameters values and change from baseline will be summarized by treatment groups at each visit for double-blind period, and by treatment sequence at each visit for on-vatiquinone period.

A subject level listing of Laboratory results will be provided for Hematology, Coagulation, Serum Chemistry, and Urinalysis, respectively.

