1.4.1. Nonclinical Safety Assessment Studies

Vatiquinone is an orally available compound that has been demonstrated in vitro and in vivo to cross the blood-brain-barrier. In 6-month (Study 1660-045) and 9-month (Study 1660-046) repeat-dose toxicity studies in rat and dog, respectively, the no observed adverse effect level (NOAEL) was 30 mg/kg/day, corresponding to Day 180 and Day 273 combined mean maximum observed plasma concentrations values of 8828 ng/mL (rat) and 12854 ng/mL (dog) and area under the plasma concentration-time curve from time zero to 24 hours values of 48,786 (rat) and

107,426 ng×h/mL (dog). The dose-limiting adverse effect in both rat and dog studies was anticoagulation as demonstrated by prolonged prothrombin time (PT) and activated partial thromboplastin time that most likely results from weak vitamin K antagonism exhibited by this class of compounds.

Vatiquinone was negative in the Good Laboratory Practice battery of genotoxicity assays including the bacterial reverse mutation Ames assay, the in vitro micronucleus assay in human peripheral blood lymphocytes, and the in vivo micronucleus assay in rats (Studies [AD75SX.503.BTL](#), [AD75SX.348ICH.BTL](#), and [AD75SX.125012ICH.BT](#)).

Safety pharmacology data collected in the 28-day toxicity studies in rat and dog and during the 6-month and 9-month toxicity studies in rat and dog, respectively, demonstrated that vatiquinone did not affect neurobehavioral or cardiovascular electrocardiogram (ECG) parameters (Studies [1660-027](#), [1660-028](#), [1660-045](#), and [1660-046](#)). In addition, vatiquinone is not a potent inhibitor of human ether-à-go-go-related gene channel current (Study [130416.FEK](#)). Vatiquinone did not influence respiratory function in rat (Study [1660-032](#)).

An in vitro phototoxicity study conducted in BALB/c 3T3 mouse fibroblasts (Study PTC743-2020-003) to assess phototoxic potential demonstrated that vatiquinone had no phototoxic potential when administered to the fibroblasts at concentrations up to 17,800 ng/mL (approximately 16 times the C_{max} obtained at the highest clinical dose of 400 mg).

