4.3. Exclusion Criteria

Subjects will be excluded from enrollment if any of the following exclusion criteria apply:

1. Allergy to vatiquinone or sesame oil
2. Aspartate transaminase (AST) or alanine transaminase (ALT) $\geq 3 \times \text{ULN}$ at time of screening
3. INR $> \text{ULN}$ at time of screening
4. Serum creatinine $\geq 1.5 \times \text{ULN}$ at time of screening
5. Participation in another interventional clinical trial 60 days prior to randomization or for the duration of this clinical trial
6. Previously received vatiquinone
7. Concomitant treatment with drug(s) that have not received regulatory agency approval for the treatment of mitochondrial diseases and use of artisanal (non-Epidiolex cannabidiol) cannabidiol therapies
8. Concomitant treatment with idebenone
9. Ongoing treatment with strong cytochrome P450 (CYP) inhibitors such as itraconazole or strong CYP inducers such as rifampin. Treatment with these agents must be completed at least 4 weeks prior to enrollment. During the study, subjects should not use grapefruit/grapefruit juice or St John's wort extract.
10. Pregnant or lactating subjects or those male or female sexually active subjects who are unwilling to comply with proper birth control methods as defined in Section 7.5.10 from the time consent is signed until 30 days after treatment discontinuation. Females of childbearing potential must have a negative pregnancy test at Screening and during the Baseline Visit.
11. Comorbidities that may confound study results (eg, fat malabsorption syndrome, other mitochondrial disorders) in the opinion of the investigator.

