7.4.5. Dose-Limiting Toxicity

No dose-limiting toxicities or other drug-related laboratory abnormalities were reported in prior clinical studies. In preclinical studies, prolongation of PT was identified as the NOAEL. Coagulation parameters (PT [can be measured as INR] and PTT) will be monitored throughout this study.

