9.3.7. Version 7.0: 06 January 2022

Overall reason for Version 7.0: The overall reason for Version 7.0 was to incorporate feedback from health authorities.

Section	Version 7.0/Update	Reason/ Rationale
Protocol	The version number and date were updated throughout. The synopsis was updated to be consistent with changes in the protocol. Editorial revisions (eg, typographical errors, punctuation, tenses, and abbreviations) were incorporated to provide clarity.	Update
Section 4.2	Inclusion criterion #2 was updated to include subjects <21 years of age. Inclusion criterion #6 was updated to "Documented medical history of epilepsy associated with mitochondrial disease for at least 6 months prior to screening except for subjects who are <2 years of age at the time of screening (Subjects <2 years of age can be considered for enrollment if all other screening criteria are met due to the potential for rapid progression in these subjects) ".	Update
Section 4.3	Exclusion criterion #3 which read, "INR \geq ULN at time of screening", was revised to read "INR >ULN at time of screening".	Update
Section 5.1.1 Section 7.1	It was corrected that weights ending in decimals ≥ 0.5 (instead of >0.5, as stated previously) should be rounded up to the next whole number for dosing calculation.	Update
Section 7.1 Section 7.1.2.8	It was specified that informed consent for subjects entering the long-term extension phase would be completed at Week 24.	Update
Section 7.1.3	It was clarified that EEG is to be collected at Week 72, as already specified in Table 2.	Clarification
Section 7.4.1	The text was updated to specify that weight could also be collected in lb and height could also be collected in inches.	Update
Section 7.4.2	The total volume of blood collected as written in V6.0 is incorrect and has now been corrected.	Update

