1.3.4.3. Laboratory Variables

- Hematology includes erythrocytes, leukocytes, and platelets.
- Coagulation includes PT and PTT reported as international normalized ratio (INR) units.
- Serum Chemistry includes liver function, renal function, electrolytes, general chemistry and lipids.
- Urinalysis includes pH, protein, glucose, ketones, blood and bilirubin.

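### SAP Table 5 reports an INR equal to ULN as a clinically significant elevation although the protocol admits it at entry, and PTT has no threshold count and the wrong unit

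*SAP*

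**What the plan says.** - **INR criteria.** SAP 6.3, Table 5 lists under elevated INR "INR $\geq \text{ULN}$ INR $\geq 1.5 \times \text{ULN", that is, two counts: at or above ULN, and at or above 1.5×ULN. The table's title calls the criteria clinically significant. Subjects are counted "at any post-baseline visit, including unscheduled visits, will be summarized for double-blind period and for on-vatiquinone period". No condition is placed on the baseline value.
- **Entry rule.** Protocol 4.3, exclusion 3 removes a subject only for "INR $> \text{ULN}$ at time of screening". The SAP is written for this version of the protocol (8.0).
- **Protocol level for INR.** Protocol 7.4.6 defines Grade 2 INR as strictly above 1.5×ULN. Protocol 7.1.9 likewise speaks of INR rising over 1.5×ULN.
- **PTT as part of the signal.** Protocol 1.4.1 describes the dose-limiting effect in rat and dog as "anticoagulation as demonstrated by prolonged prothrombin time (PT) and activated partial thromboplastin time". Protocol 1.5.1 names PT and PTT together with a level of more than 1.5×ULN. Protocol 7.4.2.2 lists PTT as a separate test in the coagulation panel.
- **PTT unit.** SAP 1.3.4.3 states "Coagulation includes PT and PTT reported as international normalized ratio (INR) units", and Protocol 2.2.4.2 says the same. Protocol 7.4.5 reads "Coagulation parameters (PT [can be measured as INR] and PTT) will be monitored throughout this study", which attaches INR to PT only.
- **Other laboratory output.** SAP 6.3 also plans values and change from baseline by visit and arm, and a subject listing of coagulation results. Protocol 8.4.6.5 promises a summary of marked abnormalities by pre-defined criteria. In the SAP, only Table 5 supplies such criteria.

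**The concern.** A safety table that calls a result clinically significant should not include results that the same trial accepts as normal at entry. As written, Table 5 does. A subject with INR at ULN at screening, at baseline and at every later visit appears as an elevated case. A reader of the study report could not tell such a subject from one whose INR rose out of the normal range.

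For PTT the problem is omission. Anticoagulation is the effect for which the protocol monitors coagulation, and the animal evidence rests on two tests. Only one of them has a threshold count. Means by visit can miss a few subjects with marked prolongation, which is what a threshold count is for. A PTT row also needs a usable unit, and both documents give one that their own descriptions of the panel tie to a different test.

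**Working it through.** The plan states no figure on this point, so there is nothing to reproduce. The check sets the rules side by side and then asks how far the size can be known.

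**1. Boundary check** (INR as a multiple of ULN)

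| INR/ULN | Accepted at entry (4.3) | Table 5, first count (≥1) | Table 5, second count (≥1.5) | Protocol 7.4.6 level (>1.5) |
|---|---|---|---|---|
| 0.99 | yes | no | no | no |
| 1.00 | yes | **yes** | no | no |
| 1.01 | no | yes | no | no |
| 1.49 | no | yes | no | no |
| 1.50 | no | yes | **yes** | no |
| 1.51 | no | yes | yes | yes |

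The rules disagree at exactly two points, 1.00 and 1.50. Elsewhere ≥ and > give the same answer. Values at ULN cannot enter the 1.5×ULN count.

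**2. The other Table 5 criteria.** ALT or AST at ≥3×ULN and creatinine at ≥1.5×ULN match exclusions 2 and 4 exactly. INR is the only parameter whose lower cut-off does not match its exclusion criterion. The amendment log (Protocol 9.3.7) records that exclusion 3 moved from ≥ULN to >ULN in version 7.0. That is context only, but it suggests where the ≥ form may have come from.

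**3. PTT.**
- Named as part of the signal: Protocol 1.4.1 and 1.5.1.
- Collected: Protocol 7.4.2.2.
- Threshold count: none in Table 5.
- Unit: INR in SAP 1.3.4.3 and Protocol 2.2.4.2; INR belongs to PT only in Protocol 7.4.2.2 and 7.4.5.

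**4. Size of the ≥ULN effect (illustration).** Let q be the chance that one INR equals ULN exactly. The documents do not give q. The Schedule of Events has four post-baseline laboratory visits in the double-blind period (Weeks 4, 8, 12 and 24), and 30 subjects per arm are planned.

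If visits are independent, the share flagged by equality alone is 1 − (1 − q)^4:
- q = 1%: 1 − 0.99^4 = 3.9%, or 1.2 of 30
- q = 2%: 7.8%, or 2.3 of 30
- q = 5%: 18.5%, or 5.6 of 30
- q = 10%: 34.4%, or 10.3 of 30

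If visits are fully correlated, the share is q itself, giving 0.3, 0.6, 1.5 and 3.0 of 30.

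**5. Dependence on reporting precision (illustration).** Assume a true mean INR of 1.0, (between-subject, within-subject) SDs of (0.05, 0.05), (0.07, 0.05) and (0.05, 0.08), screening INR ≤ULN, four draws and no drug effect. Share of subjects flagged at least once:
- Reported to 0.1, ULN 1.1: 49–65% under ≥ULN, 5–17% under >ULN.
- Reported to 0.1, ULN 1.2: 5–18% against 0.1–1.5%.
- Reported to 0.01, ULN 1.1: 20–39% against 16–34%, a ratio of about 1.2.

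The gap is therefore large or small according to a rounding rule that the documents do not state.

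**6. Does ≥ULN hide a drug effect?** Add an assumed upward shift to one arm of the 0.1-rounded model, with 30 per arm. Use Fisher's exact test at two-sided 0.05 purely as a yardstick, since the SAP plans no test here.
- ULN 1.2, shift +0.10: power 0.91–0.98 under ≥ULN, at most 0.35 under >ULN.
- ULN 1.1, shift +0.05: 0.37–0.59 against 0.25–0.36.
- ULN 1.1, shift +0.10: about equal for two SD pairs; >ULN is better for one (0.96 against about 0.85).

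In most of these settings ≥ULN separates the arms as well as or better than >ULN.

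**The case against.** The strongest reply is that these are descriptive counts of selected parameters with no decision rule, and that the lower INR cut-off is a harmless, sensitive screen. Much of this stands.

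- **A reader might infer that counting normal values masks a drug difference.** The documents do not support that, and step 6 of the working points mostly the other way. It is true that with true rates above ULN of 5% and 30% (ratio 6.0), adding equality flags at q = 5% gives 22.6% and 43.0% (ratio 1.9). But that arithmetic takes q as equal in both arms, and a drug that raises INR would move more treated subjects onto the limit.
- **A reader might infer that the coagulation signal as a whole is diluted.** It is not. The 1.5×ULN count, the level used in Protocol 7.4.6, is untouched by values at ULN.
- **A reader might infer that the plan cannot see PTT.** That is too strong. The by-visit summaries and the coagulation listing in SAP 6.3 cover the panel, and Protocol 7.4.4 has the investigator consider as AEs the clinically significant abnormalities that need active management. What is missing is the threshold count, and the by-visit summaries still need a correct unit.
- **A reader might take the anticoagulant effect as established in patients.** It is a rat and dog finding. Protocol 7.4.5 reports no dose-limiting toxicity in earlier clinical studies, and Protocol 1.4.2 reports no coagulation changes attributed to the drug.

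None of this answers the narrower point. The table gives a clinical-significance label to a value the protocol accepts, omits a test the protocol monitors for the same effect, and relies on a unit statement that other sections contradict.

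**Conclusion.** The point holds as an inconsistency in labelling and content. Three things follow from the text alone: Table 5 and the protocol disagree at INR equal to ULN and at 1.5×ULN; Table 5, the SAP's only threshold-based coagulation summary, has no PTT criterion; and the PTT unit is stated in two incompatible ways.

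The INR effect is confined to values exactly at a cut-off. Its size cannot be derived, because INR precision, the laboratory's ULN and INR variability are not given; the ranges in the working rest on assumptions. No figure can be given for PTT. No claim is made that the present rule conceals a drug difference. The change is worth making because it corrects a stated rule and adds a missing count from data already collected.

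**What to change.** 1. In SAP Table 5, set the INR criteria to >ULN and >1.5×ULN, in line with Protocol 4.3 and 7.4.6.
2. Add a PTT row at >1.5×ULN, the multiple that Protocol 1.5.1 already cites for PTT.
3. Correct SAP 1.3.4.3 and Protocol 2.2.4.2 so that PT is reported as INR, and PTT in its own units and as a multiple of its own ULN.
4. Optionally, show a shift from baseline category to worst post-baseline category for both tests. This would keep small drifts visible.

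The cost is wording and one extra table row, with no new samples. The real downside is that the first INR count becomes less sensitive to small upward drifts; the by-visit change-from-baseline summaries already planned still show these.

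Separately, Protocol 1.5.1 links changes in study drug administration to PT and PTT, while the dose-modification text and Table 3 in Protocol 7.4.6 refer to INR only. The sponsor must reconcile those passages. Nothing here proposes a dosing rule.

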6.4. Vital Signs

Vital sign (temperature, respiratory rate, systolic blood pressure, diastolic blood pressure, heart rate, oxygen saturation, weight, and BMI) and change from baseline will be summarized by treatment groups at each visit for double-blind period, and by treatment sequence at each visit for on-vatiquinone period.

A subject level listing of vital signs will be provided.

6.5. Electrocardiogram (ECG)/Electroencephalogram (EEG)

ECG results and change from baseline results (heart rate, PR interval, RR interval, QRS interval, QTc interval) along with ECG interpretations will be summarized at each visit by each assessment timepoints by treatment groups for double-blind period, and by treatment sequence for on-vatiquinone period.

Subject level listings of ECG and EEG will be provided.

6.6. Physical examinations

A subject level listing of physical examination will be provided.

6.7. Other Analyses

6.7.1. Pharmacokinetics analysis

Vatiquinone concentration will be summarized by visit and timepoint for vatiquinone subjects. Pharmacokinetics analysis will be specified in a separate document.

7. MOCK TABLES, LISTINGS, AND GRAPHS

Include a sentence that references the current protocol with the date; for SAP version 1 include [Table 1](#) with only the first row. For example:

The tables, listings, and graphs shells for the study will be provided in a separate document.

8. VERSION HISTORY

This Statistical Analysis Plan (SAP) for study PTC743-MIT-001-EP is based on the protocol Version 8.0 dated 27May2022.

SAP Version	Approval Date	Change	Rationale
1.0	23FEB2023	Not Applicable	Original version
2.0	15JUN2023	2.1.3 Per-Protocol Population: Population exclusion criteria updated. 3.1 Definition of Estimand: Details of intercurrent events added to Table 1 3.1.1 Intercurrent Events – new section added to provide details added to Table 1 5.1 Primary Endpoint(s) Analysis: Details of primary endpoint definition, sensitivity analysis, and analysis methods added.	To address FDA comments

APPENDIX 1: Schedule of Events

Procedures	Screening ^a		Baseline	Double-Blind Placebo-controlled Phase					Long-term Extension Phase								Follow-up Phase ^b
	Day -42 to 0	Day -28	Day 0 up to +7 days	Week 2 ^c ±7 days	Week 4 & 8 ±7 days	Week 12 ±7 days	Week 16 & 20 ^c ±7 days	Week 24 ±7 days	Week 28 & 32 ^c ±7 days	Week 36 ±7 days	Week 40 & 44 ^c ±7 days	Week 48 ±7 days	Week 52 & 56 ^c ±7 days	Week 60 ±7 days	Week 64 & 68 ^c ±7 days	Week 72 ±7 days	Week 77 ±7 days
Informed consent	X																
Medical history	X																
Genetic confirmation of mitochondrial disease	X																
Inclusion/exclusion criteria	X																
12-lead ECG	X		X ^d					X ^d				X ^d				X ^d	
EEG	X ^e							X								X	
Height, weight, oxygen saturation	X ^f		X		X	X		X		X		X		X		X	
Physical exam and vital signs	X		X		X	X		X		X		X		X		X	
Pregnancy test ^g	X		X		X	X		X		X		X		X		X	X
Hematology (including CBC w/diffs)			X		X	X		X		X		X		X		X	
Coagulation panel	X		X		X	X		X		X		X		X		X	
Serum chemistry	X ^h		X		X	X		X		X		X		X		X	
Urinalysis	X		X		X	X		X		X		X		X		X	
Blood samples for PK analysis ⁱ			X					X				X				X	
Train caregiver on diary completion and hospitalization log	X ^j																
AE/SAE assessment ^k	X	X	X	X	X	X	X	X	X	X	X	X	X	X	X	X	X ^l
Concomitant medications	X		X	X	X	X	X	X	X	X	X	X	X	X	X	X	
Randomization			X														
Seizure and dosing diary distribution	X																
Seizure and dosing diary collection/review		X	X	X	X	X	X	X	X	X	X	X	X	X	X	X	

Procedures	Screening ^a		Baseline	Double-Blind Placebo-controlled Phase					Long-term Extension Phase								Follow-up Phase ^b
	Day -42 to 0	Day -28	Day 0 up to +7 days	Week 2 ^c ±7 days	Week 4 & 8 ±7 days	Week 12 ±7 days	Week 16 & 20 ^c ±7 days	Week 24 ±7 days	Week 28 & 32 ^c ±7 days	Week 36 ±7 days	Week 40 & 44 ^c ±7 days	Week 48 ±7 days	Week 52 & 56 ^c ±7 days	Week 60 ±7 days	Week 64 & 68 ^c ±7 days	Week 72 ±7 days	Week 77 ±7 days
Total hospital admissions and total hospital days for disease-related issues log	X	X	X	X	X	X	X	X	X	X	X	X	X	X	X	X	
CarerQoL-7D			X		X	X		X				X				X	
PedsQL			X					X								X	
Initiate dosing diary entry			X														
In-office dosing PO with food			X ^m					X ^m				X ^m				X ^m	
Dispense study drug			X ^m			X		X ⁿ		X		X		X			
Return of study drug bottles and drug reconciliation with dosing diary						X		X		X		X		X		X	

Abbreviations: AE, adverse event; ALT, alanine aminotransferase; AST, aspartate aminotransferase; CBC, complete blood count; COVID-19, coronavirus disease 2019; ECG, electrocardiogram; EEG, electroencephalogram; eCRF, electronic case report form; PedsQL, Pediatric Quality of Life Inventory™; PK, pharmacokinetics; PO, orally; SAE, serious adverse event; w/diffs, with differentials

^a Screening will be conducted and completed in a maximum of 42 days (up to 14 days Screening and 28 days run-in period) prior to the Baseline Visit. Before the run-in period subjects will be trained in diary completion. The run-in period and initiation of the seizure diary completed during this phase of the study, will contain a minimum of 28 consecutive days of seizure data collected prior to the Baseline Visit. Ideally the subject will be instructed to start entering diary information the day after Screening, so that the requisite number of days can be collected prior to the Baseline Visit. Laboratory tests from within 30 days of Screening are acceptable for entry to the study.

^b The follow-up visit will be conducted via telephone 30 days (±7 days) after last dose or termination visit.

^c Telephone call only.

^d ECG measurement will be performed at 4 hours post dose during each visit, time-matched to PK blood collection. Electrocardiogram should be performed approximately within 10 minutes preceding the 4-hour PK blood collection.

^e EEG for epilepsy confirmation if historical EEG up to 6 months prior to screening for confirmation of epilepsy is not provided.

^f Height will only be collected at the Screening Visit; all subsequent visits will collect weight and oxygen saturation only. Any change in weight of ≥10% from Baseline should result in dose adjustment. Weights ending in decimals >0.5 should be rounded up to the next whole number for dosing calculation.

^g Female subjects of childbearing potential must have a negative serum pregnancy test at Screening and a negative urine pregnancy text at all other indicated timepoints. At-home urine pregnancy test kits will be provided; subjects will be required to perform the test at home 30 days after the last dose of study drug and self-report the results via telephone.

^h ALT, AST, and creatinine are the only chemistries required at the screening visit.

ⁱ Blood will be drawn for PK assessment predose and 1, 3, 4, and 8 hours postdose (prior to the next dose of vatiquinone) at Baseline and Week 24, and only 4 hours postdose at Weeks 48 and 72. For subjects weighing less than 10 kg, PK blood draw can be reduced to 2 timepoints per visit at the Baseline and Week 24 visits. Recommended timepoints are 0 (predose) hour and 4 hours postdose.

^j During the Screening Visit, the subject's caregiver will be trained on how to capture information in the seizure diary and hospital admissions log.

^k Serious adverse events will be assessed from the Screening Visit through 30 days following the last dose of study drug should be reported via the SAE report form to PTC within 24 hours of becoming aware of the event(s). In addition, the AE portion of the eCRF must also be completed.

^l The follow-up contact will be by telephone and should be completed 30 days (± 7 days) post last study drug administration or termination visit, whichever is later. Adverse events and SAEs will be followed until resolution or until they have normalized. At the investigator's discretion an office visit and additional tests may be conducted in order to ensure proper follow-up of an AE/SAE.

^m First dose for the double-blind phase of the study will be taken the same day as the Baseline Visit. Study drug will be dispensed during the Baseline Visit and at each subsequent in-person visit. Drug may be delivered via delivery service if needed.

ⁿ From Week 24 onwards, vatiquinone will be dispensed to all subjects entering the long-term extension phase. Vatiquinone will be dispensed after completing the Week 24 assessments. The subjects will enter the open-label phase of the study and receive vatiquinone for the dose after the visit.
